- 6.2. PATIENT REGISTRATION: Patients may be registered only after all eligibility criteria are met: see Eligibility Checklist above, and Inclusion Criteria and Exclusion Criteria CRFs (Case Report Forms). After the patient signs the Consent Form the patient is enrolled in the study, and scheduled for treatment. The pre-treatment CRFs are then filled out by the investigator and/or research assistant. This data is retained in the patient's chart and in research office. The date of registration shall be the date the consent was signed. Fiducials must be placed within 60 days, and the first fraction of radiosurgery must be administered within 90 days of registrations.

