9. PATIENT ASSESSMENTS AND TOXICITY

Assessment Preentry On tx day 4 Follow-up interval: months post therapy Years post therapy

History Physical exam (DRE) ECOG Performance Scale Prostate Biopsy & Gleason score ^a	x x x x		1 wk	1 X	3 X X X	6 X X X	12 X X X	18 X X X	24(every 6 mo up to 5 years) X ^b X ^b X ^b X	6-10
PSA	X				X	X	X	X	$\mathbf{x}^{\mathbf{b}}$	X
Prostate volume assessment Testosterone CBC, platelets BUN, creatinine	X X X X	.,	•	•	x	x	x	x	x	.,
Toxicity evaluation	X	X	X	X	X	X	X	X	$\mathbf{x}_{\mathbf{p}}$	X
AUA score	X	X	X	X	X	X	X	X	X*	X
SF-12	X			X		X	X		X*	
EPIC-26 Questionnaire	X			X		X	X		X*	X
SHIM Questionnaire	X			X		X	X		X*	X
Utilization of Sexual Rx/Devices	X			X		X	X		X*	

- a. Central review of pathology; biopsy recommended at 2 yrs, & required at time of failure
- b. Continue every 6 months through year 5
- * . Continue every 12 months through year 5.

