9.1. EVALUATION DURING TREATMENT & FOLLOWING TREATMENT

- 9.1.1. PRE-ENTRY ASSESSMENT: see section 4.7.
- 9.1.2. Stereotactic radiosurgery is an outpatient procedure. Patient management immediately after the procedure will follow routine patient care guidelines as determined by the physician. Subjects will be provided instructions on who to call with specific contact information, in the event they experience any untoward effects following treatment. In the event a subject experiences any untoward effects following CyberKnife treatment, information specific to the patient's condition and symptoms, treatment intervention required, and hospital stay and course will be recorded for purposes of clinical evaluation.
- 9.1.3. ACUTE ASSESSMENT: Patients will have toxicity evaluation and AUA score on the last day of treatment.
- 9.1.4. ASSESSMENTS FOLLOWING TREATMENT: at one week after treatment (allowed window: +/- 3 days), toxicity and AUA score will be evaluated. At 1 month (+/- 7 days) following treatment, patients will be assessed for acute toxicity, and will fill out AUA form, SF-12, EPIC-26, SHIM and Utilization of Sexual Rx/Devices. At 3, 6, 12, 18, and 24 month (+/- 2 wks) intervals (and every 6 months thereafter, through year 5), patients will be seen and evaluated, including a history, physical exam, ECOG performance status, PSA, toxicity evaluation, and AUA score. In addition, at 6 months, 12 months and annually thereafter, the SF-12, EPIC-26, SHIM and Utilization of Sexual Medications/Devices will be administered. After the 5 year follow-up patients will be seen yearly through year 10 (allowed window: +/-1 month) and the following will be performed: PSA, toxicity evaluation, and the following questionnaires will be administered: EPIC -26; AUA; SHIM. Examination and studies may

- be done at outside facility. A serum total testosterone will be measured at baseline and with every PSA through year 2.
- 9.1.5. PROSTATE BIOPSY will be performed at time of biochemical or local clinical failure, and is encouraged at 2 years following treatment and at time of distant failure.
- 9.1.6. BONE SCAN will be performed at the time of biochemical failure, or when the patient develops signs of symptoms suggesting metastatic disease.
- 9.1.7. Axial Imaging (CT or MRI) of the abdomen and pelvis will be performed at the time of biochemical failure, or when the patient develops signs of symptoms suggesting metastatic disease.

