9.3. QUALITY OF LIFE ASSESSMENTS

- 9.3.1. SF-12: The SHORT FORM-12 Health Survey measures generic health status relevant across different age, disease, and treatment groups. It provides a comprehensive, psychometrically sound assessment of health status from the patient's point of view by scoring responses to standard questions. The SF-12 is self-administered, and can usually be completed in less than 3 minutes without assistance.
- 9.3.2. EXPANDED PROSTATE CANCER INDEX COMPOSITE (EPIC)-26: is a validated comprehensive instrument developed to assess patient function and bother after prostate cancer treatment. It was developed by an expert panel of urological oncologists, radiation oncologists (including those with brachytherapy expertise), survey researchers, and prostate cancer nurses, to address symptoms related to radical prostatectomy, external beam radiotherapy, prostate brachytherapy, and hormonal symptoms. See appendix VI.
- 9.3.3. AMERICAN UROLOGICAL ASSOCIATION (AUA) SYMPTOM INDEX: Also known as the International Prostate Symptom Score (IPSS), this widely used index assesses urinary symptom bother. See appendix VI.
- 9.3.4. SEXUAL HEALTH INVENTORY FOR MEN (SHIM): is a widely used, internationally validated and sensitive instrument for assessing erectile dysfunction¹.
- 9.3.5. UTILIZATION OF SEXUAL MEDICATIONS/DEVISES: provides context for interpreting the sexual domain score of the EPIC questionnaire.
- 9.4. CRITERIA FOR DISEASE CONTROL: intervals will be measured from enrollment date.
 - 9.4.1. BIOCHEMICIAL DISEASE-FREE SURVIVAL (bDFS): is measured as time to PSA failure. While earlier reports of prostate cancer patients treated with radiotherapy have used the ASTRO consensus definition (ACD) of PSA failure, recent studies^{2,3,4} have suggested the "nadir+2" definition is a more sensitive and specific definition of biochemical failure. Indeed, a recent expert panel met in Phoenix⁵ and developed a consensus recommendation using the later definition. So that comparisons can be made with earlier literature, both definitions shall be used:

П

- 9.4.1.1.Phoenix definition: failure occurs when the PSA is 2 ng/ml more than the lowest PSA measurement before the current one, with no backdating. Administration of salvage therapy (hormones, surgery, etc...) will be considered failure.

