- 9.4.1.2.Strict ASTRO Consensus Definition (ACD): failure is defined as three consecutive rises in post-treatment PSA, measured at the specified follow-up intervals. If three consecutive PSA rises occur during the first 2 years after treatment, followed by a non-hormonal induced PSA decline, this will not be considered a failure. Administration of salvage therapy (hormones, surgery, etc...) will be considered failure. Failure date is the midpoint between the dates of the last non-rising PSA and the first PSA rise.

9.4.2. CRITERIA FOR LOCAL FAILURE:.

Clinical evidence of local progression or recurrence: Clinical failure includes a palpable abnormality that has increased in size, failure of regression of a palpable abnormality by 2 years after treatment, or redevelopment of a prostate abnormality after complete response. Patients with a prostate abnormality compatible with local recurrence, or a PSA failure shall undergo a prostate biopsy. Histologic criteria for local failure is a positive prostate biopsy more than 2 years after treatment. Patients with a normal exam and no evidence of PSA failure shall be considered controlled locally. Patients with clinical failure and no biopsy are considered local failures. If a patient is locally controlled at the time of orchiectomy or androgen ablation, he is censored and considered "not evaluable" for further local control.

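### Section 9.4.2 classifies a man with a positive biopsy more than 2 years after treatment, a normal exam and no PSA failure as both a local failure and locally controlled

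*Combined protocol and SAP*

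**What the plan says.** Section 9.4.2 sets out when a man counts as a local failure. After the clinical criteria it gives a histologic one: "Histologic criteria for local failure is a positive prostate biopsy more than 2 years after treatment". This carries no condition on exam or PSA. The sentence that follows is "Patients with a normal exam and no evidence of PSA failure shall be considered controlled locally", which carries no condition on biopsy. The only other rule there on how biopsy affects classification deals with its absence: "Patients with clinical failure and no biopsy are considered local failures".

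Biopsy is not reserved for men with suspected failure. Section 9.1.5 requires it at biochemical or local clinical failure and adds that it "is encouraged at 2 years following treatment and at time of distant failure". Footnote a to the assessment schedule in Section 9 says the same: "biopsy recommended at 2 yrs, & required at time of failure".

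The rate of local failure is a named secondary objective (Section 2). Section 11.4.2, item 1, refers back to Section 9.4 for the definition and plans descriptive summaries with confidence intervals.

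**The concern.** Two adjacent rules give opposite answers for the same man. Taken at its word, the local-control sentence scores a biopsy-proven recurrence as controlled. The purpose of an elective biopsy in a man without other signs of failure is to find disease that exam and PSA miss, yet that sentence lets exam and PSA settle the matter. Two analysts following the text could report different local failure rates from the same data.

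There is a related timing gap. The elective biopsy is set at 2 years, but the histologic criterion requires a result later than 2 years. The plan does not say how a positive result from the scheduled biopsy is to be classified.

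**Working it through.** No figure in the plan depends on this point, so there is none to reproduce. The check is to apply the Section 9.4.2 rules to every biopsy outcome in a man with a normal exam and no PSA failure.

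| Biopsy | Histologic criterion | Local-control sentence | Result |
|---|---|---|---|
| Positive, later than 2 years | Local failure | Controlled | Contradiction |
| Positive, at or before 2 years | Not met | Controlled | Controlled |
| Negative | Not met | Controlled | Controlled |
| Not done | Not applicable | Controlled | Controlled |

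Only the first row is contradictory. The second is consistent, but it is where a biopsy taken exactly on schedule would fall, and the text does not show whether that was intended.

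Other sections do not settle the first row:

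- The missing-biopsy rule in Section 9.4.2 covers clinical failure without biopsy, which is a different man.
- Section 9.4.3.2 counts biopsy as a measure of disease with no 2-year limit, but for disease-free survival, not local failure.
- Section 11.4.2 only points back to Section 9.4.

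**Size.** Inputs: 253 planned subjects (Section 11.3). Uptake of the elective biopsy, and positivity among biopsied men with a normal exam and no PSA failure, are not in the documents and are assumed.

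- One man: 1/253 = 0.40 percentage points. On the 232 men before the allowance for loss to follow-up, 1/232 = 0.43.
- Low illustration, 10% uptake and 5% positive: 253 × 0.10 × 0.05 = 1.3 men, or 0.5 points.
- High illustration, 30% uptake and 15% positive: 253 × 0.30 × 0.15 = 11.4 men, or 4.5 points.

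The product is linear in both assumptions, so doubling either one doubles the result. Within each pair of assumptions the count is an upper limit, because it treats every positive biopsy as later than 2 years and assumes that none of these men goes on to salvage therapy.

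**The case against.** The best defence is that the passage can be read coherently. The histologic criterion would govern men who have been biopsied. The two sentences after it would then be a pair of rules for men without histology: normal exam and no PSA failure means controlled, and clinical failure without biopsy means failed. That may well be the intention. But only the second of the pair is limited to men without a biopsy; the first is not, and the elective biopsy brings men with histology under it. The defence shows that the repair is small, not that it is unnecessary.

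It is also fair that the endpoint is secondary and descriptive, with no test or decision rule attached. A man given salvage therapy after a positive biopsy counts as a PSA failure under both definitions in Section 9.4.1, so the local-control sentence then no longer covers him. Both points limit the size of the problem.

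Four stronger readings are tempting, and the documents do not support them:

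- A reader might infer that the 24-month window makes the result depend on the day of biopsy. The window, "At 3, 6, 12, 18, and 24 month (+/- 2 wks) intervals", belongs to visits for history, exam, PSA and similar items. Biopsy is a separate item with no window. Any landmark splits results by date, and moving it to the start of the window would only move the edge. What remains is the mismatch between a biopsy at 2 years and a criterion later than 2 years.
- A reader might infer that the 2-year line itself is uncertain by up to 90 days, because Section 9.4 says "intervals will be measured from enrollment date" and Section 6.2 says "the first fraction of radiosurgery must be administered within 90 days of registrations". The histologic criterion names treatment as its own starting point, so this point does not rest on that difference.
- A reader might infer that the effect equals the whole expected failure rate. Section 1.15 predicts 94% PSA disease-free survival, hence 6% failure. That is biochemical failure, a different endpoint, and the illustrative 0.5 to 4.5 points run from one twelfth to three quarters of it (0.5/6 and 4.5/6).
- A reader might infer that the primary result is at risk. bDFS is defined by PSA failure or salvage therapy, so a positive biopsy reaches it only indirectly, if it prompts salvage therapy.

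**Conclusion.** The contradiction in Section 9.4.2 is real on the text, and no other section resolves it. It concerns one group: positive biopsy later than 2 years after treatment, normal exam, no PSA failure. The protocol's encouragement of a 2-year biopsy makes that group possible by design.

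Each such man shifts the local failure rate by about 0.4 percentage points. The illustration of about 1 to 11 men rests wholly on assumed uptake and positivity and should not be read as an estimate. Sample size, alpha, the efficacy criterion and the toxicity rules are untouched. The point deserves correction because the definition of a named secondary endpoint should give one answer per man.

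**What to change.** - Add a third condition to the local-control sentence in Section 9.4.2. Besides a normal exam and no PSA failure, the man must have no positive biopsy that meets the histologic criterion. The protocol's own criterion then takes precedence.
- Reconcile the biopsy timing in Section 9.1.5 and schedule footnote a with the criterion in Section 9.4.2, by stating how a positive result from the scheduled 2-year biopsy is classified.
- In the Section 11.4.2 summaries, report the local failure rate with and without failures established by biopsy alone, and give the number of men biopsied. The last two items do not correct an error. They are needed because the biopsy is elective, so the biopsy-only count depends on how many men accept it.

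The cost is a clause, a sentence and an extra row in the local-control table. No new procedure and no change in sample size is needed. The downside is that the reported local failure rate may rise slightly.

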9.4.3. CRITERIA FOR NONLOCAL FAILURE

- 9.4.3.1.DISTANT FAILURE (includes regional failure): documented if clinical, bone scan, CT or other imaging study shows metastatic disease. Biochemical failure with a negative prostate biopsy shall be considered distant only failure. Biopsy of metastatic site required if radiographic or clinical findings are equivocal. Type of metastatic failure (distant and/or regional) shall be recorded if known. Prostate biopsy recommended at this time.
- 9.4.3.2.DISEASE-FREE SURVIVAL: for any measure of disease, including PE, PSA, bone scan, CT/MRI and biopsy, or death.
- 9.4.3.3.DISEASE-SPECIFIC SURVIVAL: for any of the following:
 - 9.4.3.3.1. Death due to prostate cancer.
 - 9.4.3.3.2. Death due to other causes, with active malignancy (defined by clinical or biochemical evidence of progression). If a patient suffered a previous relapse, but has inactive disease, this is not considered a disease-specific death.
 - 9.4.3.3.3. Death due to complications of treatment.
- 9.4.3.4.OVERALL SURVIVAL: for death from any cause

10. DATA COLLECTION

See appendix IV for Case Report Forms & patient questionnaires.

11. STATISTICAL CONSIDERATIONS

- 11.1. OVERVIEW: The study's primary goals are to determine CyberKnife monotherapy efficacy and to evaluate the incidence of grade 3 or higher toxicity as stated in Section 2.0. Per RTOG/ECOG, acute toxicity will be defined as occurring within 90 days from completion of treatment. Late toxicity will be defined as occurring more than 90 days from completion of treatment. It is graded based upon Common Terminology Criteria for Adverse Events (CTCAE), v3.0., and RTOG/ECOG definitions (see appendix 5).
- 11.2. INTERIM ANALYSIS: An interim analysis was performed. The results below are based on an overall one-sided alpha of 0.05 and using the O'Brien-Fleming spendingfunction, and were calculated using nTerim (Statistical Solutions Ltd). The interim analysis is based on 4,512 months of follow-up, out of a total possible of 15,600 months (60 months* 260 Subjects). Hence the interim analysis is performed with approximately 29% of the total data possible for the final analysis. The final alpha must now be 0.04999. If the Z-score at the interim analysis exceeds 3.45701, then the trial could be stopped. If th Z-score doesn't exceed 3.45701, then the trial will continue through the primary assessment period of 5 years, where the P-value for success is at most .0499991.

	Look 1	Final Analysis- Look 2
proportion of information	0.29	1.0
Z-Score Boudary	3.45701	1.64575
Nominal Alpha	0.00027	0.049991
Incremental Alpha	0.00027	0.05

11.3. SAMPLE SIZE:

Primary Efficacy Endpoint and Hypothesis: 5-Year Biochemical Disease-Free Survival(bDFS) Among CyberKnife Treated Patients

bDFS is the primary efficacy outcome for the study. The proportion of patients disease-free within 5 years of the initial procedure is the rate of interest. The null and alternative hypotheses are as follows:

$$H_0: \pi < 90\%$$

 $H_1: \pi \ge 90\%$

 π • • is the expected proportion of CyberKnife treated patients bDFS at 5 years. The CyberKnife procedure is considered to be effective if this study's result verifies that the lower limit of the one-sided 95% confidence interval for π is not below 90%. Statistical Sample Size Derivation

Primary Efficacy Objective

We calculate the CyberKnife Treatment Group sample size, N, required to test the null hypothesis that the rate in the Treatment Group is less than 90%, against the one-sided alternative hypothesis that the rate is at least 90%...

We chose N large enough to test the null hypothesis against the alternative hypothesis with power equal to 80% at the one-sided 5% significance level.

Let Z_u denote the upper u-th percentile of the standard normal distribution. Hence $Z_{.05} = 1.645$ corresponding to the one-sided 5% level of significance and $Z_{.20} = 0.84$ corresponds to 80% power. Then the sample size is determined by Formula 1:

$$N = \frac{\left[z_{\beta}\sqrt{\pi_{1}(1-\pi_{1})} + z_{\alpha}\sqrt{\pi_{0}(1-\pi_{0})}\right]^{2}}{\left[\pi_{1} - \pi_{0}\right]^{2}}, \text{ where}$$

 π_1 is the expected proportion of CyberKnife treated patients bDFS at 5 years if the alternative hypothesis is true; the bDFS rate is then expected to equal or exceed 0.94. For purposes of sample size estimation, we require 80% power if $\pi_1 \geq 0.945$. π_0 is the expected lower limit of the 95% confidence interval for π and is set equal to 0.90. Then N= 232. Allowing 8% sample size degradation for lost to follow-up, the sample size must be increased to 232/.92 = 253 subjects.

Primary Safety Objective

The primary safety objective is to establish with 95% confidence that the percentage of CyberKnife treated patients experiencing \geq Grade 3 toxicity is not more than 5% higher than the approximately 9% 5-year rate extrapolated from Table 2, Section 1.15.

With N=232 CyberKnife treated subjects, if the observed \geq Grade 3 toxicity rate equals 9%, then with 95% confidence the "true" rate \leq 12.6%. Since the difference between 12.6% and 9% is less than 5%, the sample size of 232 subjects is more than large enough to meet the primary safety objective.

11.3.1 ACCRUAL RATE: the initial three months while institutions are obtaining IRB approval, therefore we do not expect to meet the targeted monthly accrual rate until after the first three months. The estimated accrual rate is 2 patients per study site per month. Expectations of 5 treating study sites assumes an accrual period of approximately 29 months total.

11.4STATISTICAL METHODS

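### The interim efficacy boundary counts person-months as information on a 5-year proportion and leaves the interim Z undefined, so its stated error level has no basis

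*Combined protocol and SAP*

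**What the plan says.** Section 11.2 reports that an interim analysis was performed, "based on an overall one-sided alpha of 0.05 and using the O'Brien-Fleming" spending function. Its information fraction comes from follow-up time: "The interim analysis is based on 4,512 months of follow-up, out of a total possible of 15,600 months (60 months* 260 Subjects"). From this the section concludes: "Hence the interim analysis is performed with approximately 29% of the total data possible for the final analysis". The table gives an interim boundary of 3.45701 (nominal alpha 0.00027) and a final boundary of 1.64575. The consequence of crossing is permissive: "If the Z-score at the interim analysis exceeds 3.45701, then the trial could be stopped".

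Section 11.3 defines the primary endpoint: "The proportion of patients disease-free within 5 years of the initial procedure is the rate of interest". Section 11.4.1 tests it with a one-sided 95% Wilson lower limit on the observed proportion, which must not fall below 90%. That formula has no term for censoring. Kaplan-Meier curves appear in 11.4.2, under the secondary survival objective.

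The plan does not say which statistic supplies the interim Z, how patients with less than 60 months of follow-up are counted, or how many patients contributed to the 4,512 months.

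**The concern.** A spending-function boundary holds its error rate only if the information fraction describes the statistic being monitored. For a proportion at 5 years, a patient seen for 17 months without failure does not supply 17/60 of an observation. His 5-year status is unknown. Person-months are a reasonable measure of information for a constant-hazard rate, but the plan does not test a rate.

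With Z undefined, the same printed boundary can be practically inert or far too easy to cross, depending on how it is applied. What is at stake is an early efficacy stop, or an early efficacy claim, made at a level that the stated 0.027% does not describe.

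**Working it through.** **Inputs.** From 11.2: 4,512 and 15,600 months, 260 patients, fraction 0.29, boundary 3.45701. From 11.3: null rate 0.90, 232 evaluable and 253 enrolled patients, accrual of about 29 months. Assumption: constant hazard. The protocol uses a constant failure rate for its own projection of one cited series (Table 1 footnote) but states no shape for the interim.

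**1. The plan's boundary reproduces.** 4,512/15,600 = 0.289, rounded to 0.29. One-sided O'Brien-Fleming spending gives alpha(0.29) = 2[1 − Φ(1.960/√0.29)] = 2[1 − Φ(3.640)] = 0.000273, so Z = 3.45701. The final bound is 1.64575. The boundary therefore rests entirely on the person-month fraction.

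**2. Follow-up at the look.** If all 260 contributed, mean follow-up is 4,512/260 = 17.4 months. With even entry over 29 months the range is 17.4 ± 14.5, about 3 to 32 months. Nobody has then reached 60 months, and a Kaplan-Meier curve cannot be read at 60. Whatever the entry pattern, no more than 4,512/60 = 75.2, that is 75 patients, can have completed 60 months.

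**3. Reading A: completers only, score Z.** This is the test that the Wilson limit inverts. With 75 of 75 disease-free, Z = (1 − 0.9)/√(0.09/75) = 2.89. Crossing needs n ≥ (3.45701 × 0.3/0.1)² = 107.6, so 108 completers, all disease-free. The exact version needs 78, and 75/75 gives p = 0.9^75 = 0.00037, above 0.00027. The boundary is out of reach.

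**4. Reading B: person-time rate.** λ = −ln(0.9)/60 per month. Expected failures at a true 90% are E = 4,512 × λ = 7.92.
- Score Z with zero failures: √7.92 = 2.81. Not reachable.
- Exact p with zero failures: e^(−7.92) = 0.00036, above 0.00027. Not reachable.
- Signed likelihood-ratio Z: √(2 × 7.92) = 3.98 with zero failures, 3.12 with one. It crosses only with zero failures, probability about 0.04% at a true 90%.

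**5. Reading C: 11.4.1's crude proportion over all 260, not yet failed counted as disease-free.** With null variance, crossing requires failures ≤ 260 × (0.1 − 3.45701 × √(0.09/260)) = 9.28, so 9 or fewer. At a true 90%, P(Poisson(7.92) ≤ 9) = 72.6%. At a true 85%, E = −4,512 × ln(0.85)/60 = 12.22 and the probability is 22%.

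**6. Range for reading C at a true 90%.**

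| Assumption varied | P(cross) |
|---|---|
| Base case (Poisson) | 73% |
| Binomial, staggered entry | 75% |
| Weibull shape 0.5 / 0.75 / 1.5 / 2 (staggered entry) | 11% / 42% / 98% / 99.9% |
| n = 253 / 200 / 150 (thresholds 8 / 5 / 2 failures) | 60% / 20% / 1.5% |
| Plug-in (Wald) variance, n = 260 (13 or fewer failures) | 97% |

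For the n rows, expected failures stay at 7.92 because the person-months are fixed; only the threshold moves. Every entry is well above 0.027%: the smallest, 1.5%, is about 54 times that level.

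**The case against.** The best defence has four parts.

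First, no passage says that patients with short follow-up count as successes. That rule is one way of filling a gap. Section 9.4.1 measures bDFS as time to PSA failure, and 11.4.2 plans periodic Kaplan-Meier curves for survival as defined in Section 2.0, which includes bDFS. A censored estimate is therefore within the plan's vocabulary. This stands, but 11.4.1 does not use it for the primary test and 11.2 does not use it for the interim Z.

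Second, the number of patients contributing at the look is not stated. The 260 appears only in the denominator, and at n = 150 the crossing probability falls to 1.5%. This stands too, which is why 73% must carry its conditions.

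Third, the readings above are not exhaustive. A likelihood-ratio person-time Z can cross with zero failures. A Wald Z on completers could cross at 73 of 75, although evenly spread accrual would supply no completers. A reader might infer that the boundary can never be reached; that is true only of the score and exact forms shown.

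Fourth, the look is already done, stopping is permissive, and the final test hardly changes: the critical value moves from 1.645 to 1.64575. A reader might infer that the trial's 5% error has actually been inflated. The documents do not support that, since they do not show that any stop or claim rested on a crude proportion. What remains is that the current text still presents crossing 3.45701 as grounds to stop.

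**Conclusion.** The concern holds in a limited form. The 0.29 is not the information on the quantity that 11.3 and 11.4.1 test, and the interim Z is not defined. This is a stated rule resting on the wrong quantity, not only missing detail.

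The size depends on the reading. On completers, or on a person-time score, the boundary is out of reach. On a person-time likelihood ratio it is crossed about 0.04% of the time at a true 90%. On the crude proportion with patients not yet failed counted as disease-free, it is crossed about 73% of the time, given constant hazard, null variance and n = 260. The 73% illustrates one reading; it is not the trial's established type I error. The direction, far above 0.027%, survives every variation of that reading tried here.

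Only 0.00027 of alpha is involved for the final analysis, so the consequence is confined to the stopping decision and any early efficacy claim. The change should be made, but the final test is not in doubt on this account.

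**What to change.** In 11.2, state that no efficacy stop and no efficacy claim rests on this look, and keep the final critical value of 1.64575. Alpha already spent should not be taken back after the look has been performed, and keeping it costs almost nothing.

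If a boundary is retained, define the interim Z on a Kaplan-Meier 5-year bDFS estimate, set the information fraction as the ratio of inverse variances of that estimate (interim to final), and recompute the boundary. Such an estimate exists only once some follow-up reaches 60 months. With 260 patients entered evenly over 29 months, it would not have existed at this look.

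Either change is a matter of wording and needs no new data. The downside is that the sponsor gives up an early efficacy stop, but one that the design cannot validly support.
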